### 2.2 POINT ABSTINENCE (FROM CC) AT SIX MONTHS POST SWITCH

A secondary outcome will be 7-day point abstinence at 6 months post-switch, for participants who are smoking abstinent during weeks 8-11 post-quit, as defined above in Section 2.1. This will be assessed by self-report utilizing an automated SMS messaging system.

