### **8.4 6-MONTH FOLLOW UP**

Participants who complete the study will be contacted six months after the switch day utilizing an automated SMS messaging system, to ascertain their current smoking status and use of e-cigarettes. If a participant self-reports current abstinence from smoking they will be asked to return to the office for collection of an expired air CO for verification.

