## 8.6 SMS MESSAGING

8.6.1 Daily SMS Message (after screening, prior to V2) – Participants will receive a text with a link to a survey to access the following:

- Have you smoked any combustible cigarettes today?
  - If yes, how many cigarettes did you smoke?
  - What was your favorite cigarette of the day?  
1-First one, 2-One immediately after a meal, 3-Any other cigarette

8.6.2 Daily SMS Message (From Visit 2) -- Participants will receive a text with a link to a survey to assess the following:

- Have you smoked any combustible cigarettes today?
  - If yes, how many cigarettes did you smoke?
  - Which cigarette did you smoke today? (If only 1 cigarette is reported)  
1-First one of the day, 2-One immediately after a meal, 3-Any other cigarette
  - What was your favorite cigarette of the day? (Of more than 1 cigarette is reported)  
1-First one, 2-One immediately after a meal, 3-Any other cigarette
- Have you used your e-cigarette today?
  - If yes, how many times did you use your e-cigarette today?
- Did you take your study drugs this morning? (After Visit 3)

8.6.3 6-Month follow up SMS Message -- Participants will receive a text with a link to a survey to assess the following:

- Have you smoked a combustible cigarette since your last visit?
  - If yes, are you still smoking combustible cigarettes right now?
  - How many combustible cigarettes do you smoke per day on average?
- Have you used an e-cigarette since your last visit?
  - If yes, are you still using an e-cigarette?
  - How often do you use an e-cigarette?
- Have you used any other nicotine containing products (other than e-cigarettes) since you last visit?

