## 13.1 OUTCOMES

### 13.1.1 Switching Outcome

Complete switching from combustible cigarette use at each time point will be defined by a self-report of no cigarette smoking (not even a puff) since the prior session, confirmed by an expired air CO reading of less than 5 ppm. The primary switching outcome will be smoking abstinence during weeks 8-11 post-switching date. An intent-to-treat approach will be taken in which any participants lost to follow-up after the point of randomization, or who have smoked during weeks 8-11 will be counted as having not completely switched to e-cigarette use. A secondary outcome will be 7-day point abstinence at 6 months post-switch. The main goal of the 6-month follow-up is to assess the persistence of switching to e-cigarettes. The main hypothesis to be evaluated in this pilot study is that the rate of complete switching to e-cigarette use will be greater than the historical benchmark of 45% smoking abstinence expected with varenicline when it is used in smoking cessation treatment.

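### The 6-month SMS has no past-7-day question, so the 7-day abstinence outcome cannot be scored for someone who lapsed after V7 and then stopped

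*Combined protocol and SAP*

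**What the plan says.** Section 2.2 defines the outcome and its population: "A secondary outcome will be 7-day point abstinence at 6 months post-switch, for participants who are smoking abstinent during weeks 8-11 post-quit". On measurement it says: "This will be assessed by self-report utilizing an automated SMS messaging system". Section 13.1.1 restates the outcome, "A secondary outcome will be 7-day point abstinence at 6 months post-switch", without a scoring rule and without repeating the restriction to week 8-11 abstainers. The same section defines complete switching at each time point by a self-report of no smoking "since the prior session, confirmed by an expired air CO reading of less than 5 ppm".

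The 6-month script is in Section 8.6.3. It has three cigarette items. The first is "Have you smoked a combustible cigarette since your last visit". The second, put to those who say yes, is "If yes, are you still smoking combustible cigarettes right now". The third asks for average cigarettes per day and gives no reference period.

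Section 8.4 describes the contact as being made "to ascertain their current smoking status and use of e-cigarettes". It adds a check: "If a participant self-reports current abstinence from smoking they will be asked to return to the office for collection of an expired air CO". It names no 7-day window and no further question for that visit.

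**The concern.** The outcome needs one fact: whether the participant smoked in the 7 days before the 6-month contact. The script asks about a much longer window and about the present moment, but not about that week.

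The omission falls where the 7-day definition does its work. Among people abstinent at V7, 7-day abstinence differs from no smoking since V7 mainly for those who lapsed and later stopped, and those are the people the script cannot place. An analyst would have to choose a rule after the data are in. Scoring on present smoking could over-count abstinence. Scoring on smoking since the last visit could over-count failure. Section 13.1.1 gives persistence of switching as the main purpose of the 6-month follow-up, so the reported persistence rate could depend on that choice.

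**Working it through.** The plan states no figure for this outcome, so there is none to reproduce. The check is whether the answers determine 7-day status, and how far the rate can move where they do not.

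**Step 1. Answer paths in Section 8.6.3**

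| Since last visit | Smoking now | 7-day status |
|---|---|---|
| No | not asked | Abstinent |
| Yes | Yes | Reasonably scored as smoking, although an occasional smoker with a clear week would be misscored |
| Yes | No | Undetermined |

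The cigarettes-per-day item does not resolve the third row: an answer of zero does not date the last cigarette.

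**Step 2. How long the look-back is**

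Inputs: e-cigarette use starts at V2 and study drugs at V3, one week later (Section 3.1); the switch is about 7 days after drug start (participant instruction sheets for bupropion and zonisamide); product use lasts 13 weeks (Section 5.3); the visit window is 4 days either way (Section 4.8.2). Assumptions: V2 is week 0, so the switch is at week 2 and V7 at week 13; six months is 182 days.

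Look-back = 182 − (13 − 2) × 7 = 182 − 77 = 105 days, or 101 to 109 days with the visit window. The outcome needs 7.

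**Step 3. Other planned sources**

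- The smoking-status SMS stops at End of Study (Section 8.2.14.14).
- The ABOUT questionnaire has past-7-day items, but they cover all tobacco and nicotine products together, and it is scheduled only at V2, V3 and V7 (Section 8.5, Appendix 14).
- The Schedule of Events has no 6-month column.
- The Section 8.4 office visit is described as CO collection only.

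None of them supplies the missing answer.

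**Step 4. Effect on the rate**

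With u participants in the undetermined row and n week 8-11 abstainers, the 6-month rate is undetermined over a span of u/n. The documents give no value for u, so the table shows u = 1. It takes n as the number counted as switched at V7, which is an assumption.

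| Outcome under Section 3.1 | n | 100/n, points per participant |
|---|---|---|
| Advance after the first 25 (at least 16) | 16 to 25 | 6.3 to 4.0 |
| Expand, then advance (at least 28 of 50) | 28 to 40 | 3.6 to 2.5 |
| Expand, then fall short | 13 to 27 | 7.7 to 3.7 |
| Stop after the first 25 | 12 or fewer | 8.3 or more |

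The maximum of 40 arises because expansion requires 13 to 15 switchers in the first 25, and 15 + 25 = 40. The 12 is the largest count below the 13/25 needed to expand. The upper ends of 25 and 40 need every participant at a stage to switch.

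**The case against.** **The group is narrow.** It contains only people abstinent in weeks 8-11 who smoked after V7 and had stopped again by month 6. It could be empty, and 1/n per person holds for any binary outcome. This stands as a limit on size: a possible error is shown, not an expected one, and it concerns one secondary outcome of a small single-group study.

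**The CO visit reaches these people.** Anyone reporting current abstinence is invited back under Section 8.4, so staff could ask about the past week. That is a real opportunity, but the plan does not call for the question. In Section 13.1.1 CO confirms a self-report; it does not replace one.

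**The script matches another definition in the plan.** Its first item fits the look-back to the prior session in Section 13.1.1, under which the disputed participant has simply not switched. The match is genuine and makes the script usable for abstinence since V7. That is a different outcome from the 7-day one, which both sections name separately.

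**The remedy could be smaller.** One question cures the defect. The CO trigger, the parallel CO-verified rate and the clarifying text are separable. Using 7-day abstinence as the trigger would also end CO checks in people who stopped within the past week. Non-response is partly covered, since Section 13.1.1 already counts participants lost to follow-up as not switched. These points are fair, but they concern the extent of the change and not the need for the question.

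**Conclusion.** The concern holds. Followed exactly, the plan cannot score its own 6-month secondary outcome for a participant who smoked after V7 and is not smoking when contacted. Participants with no smoking since V7 can be classified, and those still smoking reasonably so, so the outcome is partly, not wholly, unmeasurable. Each undetermined participant is worth 6.3 to 4.0 points if the study advances after 25 and 3.6 to 2.5 points if it advances after 50. These figures rest on equating week 8-11 abstainers with those counted as switched at V7. No total is claimed. The change should be made, but nothing about the primary outcome, the sample size or the V7 rule depends on it.

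**What to change.** Before the first 6-month contact, add one item to Section 8.6.3: *In the past 7 days, have you smoked a combustible cigarette, even a puff?* Score the 6-month outcome from it. Every responder is then classified and the ambiguity falls to zero.

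Accompanying clarifications, which can be adopted separately:

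- **Section 2.2:** keep the self-report result and count SMS non-responders as not abstinent. Alongside it, report a CO-verified result with the existing cut-off of less than 5 ppm, counting self-reported abstainers without a reading as not verified.
- **Section 8.4:** use a no to the new item as the trigger for the CO visit. If CO readings are also wanted from people who stopped within the past week, the present trigger can stay, because scoring no longer depends on it.
- **Section 13.1.1:** repeat the week 8-11 abstainer denominator and state that the look-back to the prior session does not apply at 6 months.

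The cost is one SMS question, short text in three sections and IRB approval before implementation (Section 14.1). The CO visit and its $25 payment (Section 4.7) already exist. The CO-verified rate may come out below the self-report rate.

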## 9 RISK / BENEFIT INFORMATION

---

### 9.1 POTENTIAL RISKS

Continuing to smoke carries significant health risks; however, the participants in the studies will have expressed an interest in switching from smoking combustible cigarettes to using an electronic cigarette during the brief study duration, and hence will not be exposed to significant additional risks.

#### 9.1.1 Zonisamide

The most common adverse effects of zonisamide include somnolence, dizziness, nausea, heartburn, constipation, weight loss, changes in taste, dry mouth, drowsiness and headache. In prior clinical trials of zonisamide, discontinuation rates varied between 4% to 24% due to adverse effects (these studies

administered daily doses of 300 to 500 mg). This study will evaluate zonisamide at a maximum dose of 100 mg daily.

### 9.1.2 Bupropion

Common adverse effects of bupropion (occurring greater than 5% more than placebo) include headache, dry mouth, nausea, insomnia, constipation, and dizziness. These adverse effects were observed for doses ranging from 300 mg to 400 mg daily. Adverse events leading to discontinuation in clinical trials occurred at a relatively low rate, with 7% drop-out for all doses, 9% drop-out at the 300 mg dose, and 11% drop-out for the 400 mg dose. This study will utilize bupropion at a maximum dose of 300 mg daily.

### 9.1.3 Use of Halo G6

The common risks associated with e-cigarette use include coughing, dry mouth, throat irritation, sore throat and shortness-of-breath.

### 9.1.4 Tobacco Withdrawal

To the extent that nicotine or other tobacco smoke constituent intake is reduced or eliminated, participants may experience tobacco withdrawal symptoms, including craving, difficulty concentrating, mood disturbance and increased appetite/weight gain.

### 9.1.5 Nicotine Toxicity

The e-cigarette may deliver less of various tobacco smoke constituents than participants' usual brands of cigarettes, and in some cases, may deliver more nicotine. However, participants control their nicotine intake and many studies have shown that smokers effectively limit their nicotine intake from cigarettes to avoid symptoms of nicotine toxicity (e.g., nausea, vomiting, sweating, headache, dizziness, jittery, palpitations, or in the case of extreme cases of nicotine overdose, convulsions, respiratory paralysis and death).

### 9.1.6 Blood Draw

The risks associated with venipuncture are minimal and include momentary discomfort and/or bruising. Infection, excess bleeding, clotting, and fainting are also possible, although unlikely.

## 9.2 PROTECTION AGAINST RISKS

The risks to which participants will be exposed are comparatively minor, because it is unlikely when using the e-cigarette that they will be exposed to higher levels of toxicants than when smoking their cigarettes. Smokers are very experienced in regulating their nicotine intake to avoid excessive amounts. Additionally, participants will be screened medically and monitored throughout the study.

Study participants will receive detailed instructions on the use of the tobacco products distributed to them, in order to minimize the possibility of misuse. Participants will be instructed to keep all nicotine/tobacco products away from children and pets.

Participants will be instructed to report any side effects to study staff, who will communicate these reports to the medical staff. The most appropriate course of action will be determined, which may include options for termination of exposure to study-related clinical materials (e.g., e-cigarettes), options for dose modifications to study drugs, or complete termination of study drugs. Participants will,

however, be reminded that they have the option to withdraw from the study at any time. Participants will also be given a 24-hour emergency contact number in the event that side effects or adverse events occur between sessions.

## 10 QUALITY CONTROL AND QUALITY ASSURANCE

---

### 10.1 TRAINING OF STAFF

The Investigator or designee will ensure that appropriate training relevant to the study is provided to all staff involved in the study, and that any new information relevant to the performance of this study is forwarded in a timely manner to the staff.

### 10.2 AUDITS AND INSPECTIONS

Good Clinical Practice regulations require independent inspections of clinical program activities. Such inspections may be performed at any time before, during, and after the study.

Authorized representatives of the Sponsor, regulatory agencies and/or an IRB may perform audits or inspections, including source data verification. The purpose of an audit or inspection is to systematically and independently examine all study-related activities and documents to determine whether these activities were conducted, and data were recorded, analyzed and accurately reported, according to the protocol, ICH/GCP guidelines and any applicable regulatory requirements. The Investigator or designee will contact the Sponsor immediately if contacted by a regulatory agency about an inspection at their site.

The Investigator and study staff are responsible for maintaining a comprehensive and accurate filing system of all study-related documentation that will be suitable for inspection at any time by the Sponsor, its authorized representative, and other regulatory agencies.

## 11 REPORTING OF ADVERSE EVENTS

---

### 11.1 DEFINITIONS

#### 11.1.1 Adverse Event

An Adverse Event (AE) is defined as any untoward medical occurrence that may present during participation in the study and which may or may not have a causal relationship with study procedures and/or products tested in this study. An adverse event (AE) can therefore be any unfavorable and unintended sign (including an abnormal laboratory finding, for example), symptom, or disease temporally associated with the use of a medicinal product, whether or not considered related to the study procedures and/or products.

Any increase in the severity and/or the frequency of a concomitant disease is considered an AE.

### 11.1.2 Serious Adverse Event

A Serious Adverse Event is any adverse event that:

- results in death;
- is life-threatening;
- results in inpatient hospitalization or prolongation of existing hospitalization;
- results in persistent or significant disability / incapacity;
- results in a congenital anomaly / birth defect;
- requires immediate medical or surgical intervention.

Important medical events that may not result in death, be life threatening, or require hospitalization may be considered an SAE, when, based on appropriate medical judgment, the event may jeopardize the participant, or the participant may require medical or surgical intervention to prevent one of the outcomes listed in the above definitions.

The term "life-threatening" in the definition of "serious" refers to an event in which the participant was at risk of death at the time of the event; it does not refer to an event, which hypothetically might have caused death if it were more severe.

Any pre-planned hospitalizations that are known at the time of signing the ICF will not be recorded as an SAE; however, they will be recorded as AE only. Any AE that occurs during this pre-planned hospitalization will be considered according to the above definitions.

## 11.2 COLLECTION OF SAFETY EVENTS FROM PARTICIPANTS

Information recorded when collecting AEs will include: thorough description of the AE, seriousness assessment, start and stop dates (if known), circumstances leading up to the event, clinical elements such as clinical course, specific vital signs and test results that may explain the pathophysiology of the event, as well as alternative explanations to its occurrence, the action taken with the investigation product/procedures due to the AE, the participant's disposition in the study after the occurrence of the AE and the final outcome of the AE (if known).

Any exacerbation/worsening or increased frequency of an AE or pre-existing condition shall be evaluated and recorded.

AEs should be collected using interviews with the participant.

Whenever a medically meaningful diagnosis is available to comprise a set of reported signs and/or symptoms, it should be preferentially provided as the AE or SAE term, rather than the individual signs and/or symptoms. Otherwise, each one of those signs and/or symptoms should be reported separately as event terms.

### 11.2.1 Period of Collection

All existing health conditions identified during the Screening Period will be recorded as concomitant disease and the participant's eligibility will be reviewed. Any AEs which occur during the screening session will be captured by the study site staff and assessed by the Investigator or designee in order to establish relationship or relatedness in respect to study procedures.

Any new, clinically relevant, abnormal finding detected during the study or worsening of a pre-existing condition/concomitant disease will be documented as an AE or an SAE.

All ongoing AEs at the End of Study participation will be followed-up by the Investigator or designee until they have improved, resolved, stabilized (i.e., no worsening of condition), or until an acceptable explanation has been found. The Investigator or designee will refer the participant to their Primary Care Provider for follow up of those AE when appropriate.

## 11.3 ASSESSMENT OF ADVERSE EVENTS

### 11.3.1 Intensity of Adverse Events

For each AE/SAE, the intensity will be graded on a 3-point intensity scale:

- Mild: The AE is easily tolerated and does not interfere with daily activity.
- Moderate: The AE interferes with daily activity, but the participant is still able to function.
- Severe: The AE is incapacitating and requires medical intervention.

### 11.3.2 Relationship to Study Procedures

In general, all AEs and SAEs will be assessed by the Investigator or designee as either 'related' or 'not related'.

- Not related: The temporal relationship of the clinical event to study procedures and/or the study medication makes a causal relationship unlikely, or, concomitant medication, therapeutic interventions, or underlying conditions provide a sufficient explanation for the observed event.
- Related: The temporal relationship of the clinical event to study procedures and/or the study medication makes a causal relationship possible, and concomitant medication, therapeutic interventions, or underlying conditions do not provide a sufficient explanation for the observed event.

### 11.3.3 Expectedness Assessment

All AEs and SAEs will be assessed by the Investigator or designee as either 'expected' or 'unexpected'. The determination of expectedness for an event is based upon the judgement of the Investigator (or designee). An 'unexpected' AE/SAE occurs with a nature/severity/incidence that has not previously been observed or reported and is inconsistent with the known risk information described in literature and/or as listed in this protocol.

## 11.4 FOLLOW-UP OF NON-SERIOUS AND SERIOUS ADVERSE EVENTS

All ongoing Non-Serious AEs at the End of Study participation will be followed-up by the Investigator or designee until they have improved, resolved, stabilized (i.e., no worsening of condition), or until an acceptable explanation has been found. The Investigator or designee will refer the participant to their Primary Care Provider for follow up of those AE when appropriate.

Serious AEs will be followed up by the Investigator or designee, despite their continuation after the End of Study, until their resolution, stabilization (i.e., no worsening of the condition), or an acceptable explanation has been found (e.g. a chronic condition).

### 11.5 REPORTING OF SAFETY EVENTS TO IRB

The Principal Investigator will report all serious adverse events relating to the study in an expedited manner to the Institutional Review Board (IRB) office in accordance with the Center's standard operating procedures and GCP reporting guidelines.

### 11.6 REPORTING OF SAFETY EVENTS TO FDA

The Principal Investigator will report any suspected adverse reaction to study treatment that is both serious and unexpected to the FDA following established Safety Reporting guidelines.

